5 STUDY POPULATION

Our study population will consist of patients on the registries of AltaMed's 12 Los Angeles County primary care clinics, and we will draw a simple random sample of 1000 patient households without replacement. Patients will be randomly selected by address and confirmed to be patients by medical identification number. All members of

the household, both adults and children over the age of 5, are invited to participate in testing, but at least one parent and one child must participate in order for the household to qualify. Partnering with FQHCs will build trust and also provide us access to reliable contact information. In a pilot study at a FQHC, we were able to recruit over 50 families for antibody testing within just 2 days.

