9.2 SAMPLE SIZE DETERMINATION

We will recruit a cohort of 2,160 people (540 families), and stratify into 3 subgroups based on predictors of commitment to participation in testing programs. Randomization will be clustered by family. Sub-group membership will be based on the mean household survey response to the survey component. For the purposes of power analyses, we assume high Intra Cluster Correlation within family on uptake of repeat testing (>0.90).

Stratified Allocation Plan and Power Analysis (540 households, 2160 individuals)		
	Control	Intervention
Stratification	# households	# households
HTE Subgroup 1	60	60
HTE Subgroup 2	60	60

HTE Subgroup 3	60	60
% Seropositive in Baseline Test	10%	10%
Total Households Per Arm	180	180
Projected Average Treatment Effect Size	Reference Group	Reference+10%
Minimum Detectable Effect Size Compared to Controls (H4r)	±3%	
Detectable 3-subgroup HTE and Seropositivity (H1r, H2r, H3r)	±7%	

Assuming a similar effect size to prior studies in similar populations, we expect a 10 percentage point difference in repeat testing adherence between intervention and control groups. With 540 households, we are powered to detect as little as 3 percentage point difference between interventions and controls in the 540 households we will enroll. To assess heterogeneity of treatment effects (THE), there is more than 80% power to detect a between-subgroup difference of 7 percentage points, assuming 180 households in each sub-group.

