9.3 POPULATIONS FOR ANALYSES

Sampling low-income populations is important for research on disparities, however, recruiting this population is challenging because they often lack consistent contact information, do not have internet access, and mistrust research. We will use a novel way of recruiting this population by partnering with AltaMed Health Services, the largest FQHC in the United States that serves overwhelmingly a low-income and minority population Partnering with an FQHC will build trust and also provide us access to reliable contact information.

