$$\pi = \beta_0 + \beta_1 x_{ij} + \eta_j + \varepsilon_i \quad [3]$$

For Hypothesis 3r, we will use a simple mixed-effects logistic model, where $\pi = \ln\left(\frac{p}{1-p_i}\right)$, is the probability of Time 2 attendance by individual i in household j given they attended Time 1 testing; β_1 is seropositivity status at Time 1 (yes vs. no); and η_j is the random intercept for each household capturing household-level effects.

We will use two separate models for Hypothesis 4r.

$$\pi = \beta_0 + \beta_1 x_{ij} + \beta_2 x_{ij} + \beta_3 x_{ij} + \beta_4 x_{ij} + \beta_5 x_{ij} + \eta_j + \varepsilon_i \quad [4a]$$

Model 4a will assess the probability, $\pi = \ln\left(\frac{p}{1-p_i}\right)$, of testing attendance for individual i in household j , where β_1 is the main effect for testing time (reference = Time 1); β_2 is the main effect for Financial Incentives (reference = lottery condition); β_3 is the main effect for Messaging (reference = personal); β_4 is the interaction between testing time and Financial Incentives; β_5 is the interaction between testing time and Messaging; and η_j is the random intercept for each household.

$$\pi = \beta_0 + \beta_1 x_{ij} + \beta_2 x_{ij} + \beta_3 x_{ij} + \beta_4 x_{ij} + \beta_5 x_{ij} + \beta_6 x_{ij} + \beta_7 x_{ij} + \eta_j + \varepsilon_i \quad [4b]$$

Model 4b will assess the probability, $\pi = \ln\left(\frac{p}{1-p_i}\right)$, of testing attendance for individual i in household j , where β_1 is the main effect for testing time (reference = Time 1); β_2 through β_4 are the main effects for study arm (personal messaging and loss protection, family messaging and lottery, family messaging and loss protection), where personal messaging and lottery is the reference group; β_5 through β_7 are the interactions between study arm and testing time; and η_j is the random intercept for each household.

For Models 4a and 4b, we will use unrestricted random sampling to select 3,000 observations, 2,000 times, clustered by household to bootstrap 95% confidence intervals for probability differences. We

will test differences in effect sizes for Model 4a (β_4 vs. β_5) and 4b (β_5 vs. β_6 ; β_5 vs. β_7 ; β_6 vs. β_7) using equality of regression coefficients tests.⁶ We will also calculate the inverse of observed probabilities to derive the Number Needed to Intervene on (NNI), and calculate standard errors by taking the square root of $P * (1 - P)/N$.⁷

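### The bootstrap for Models 4a and 4b draws a fixed 3,000 observations, with no stated unit and no link to the analysed dataset, so the H4r intervals have the right width only by coincidence

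*Combined protocol and SAP*

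**What the plan says.** Section 9.4.1 contains the only bootstrap instruction in the documents, and it applies to both versions of Model 4: "we will use unrestricted random sampling to select 3,000 observations, 2,000 times, clustered by household to bootstrap 95% confidence intervals for probability differences". No origin for 3,000, interval type or rescaling is given.

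Both models describe the probability "of testing attendance for individual i in household j". In each, the first coefficient "is the main effect for testing time (reference = Time 1"), so a person can contribute a row at each of two testing times.

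Section 9.2 gives the planned size: "We will recruit a cohort of 2,160 people (540 families"), a mean of 4 per household. It adds "Randomization will be clustered by family", and for power, "we assume high Intra Cluster Correlation within family on uptake of repeat testing (>0.90"). Section 5 sets a lower bound on household size, because "at least one parent and one child must participate in order for the household to qualify".

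Three places bear on which rows enter the models:
- Section 9.3, headed as the analysis populations, describes recruitment ("We will use a novel way of recruiting this population by partnering with AltaMed Health Services") and defines no analysis set.
- Section 7.1 follows the whole cohort that completed the baseline survey, including those who declined the first wave, and offers them the second wave.
- Section 9.1 introduces the retesting hypotheses, 4r among them, as relative to people who took a first test.

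**The concern.** Bootstrap spread reflects how many independent units each resample contains. Here the independent unit is the randomised household. A resample with fewer households than the data gives intervals that are too wide, and one with more gives intervals that are too narrow, unless the result is rescaled. A constant of 3,000 breaks the link between the size of the trial and the width of its intervals.

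These are the intervals specified for the H4r probability differences, which address the primary objective of whether incentives and messaging raise repeat testing. Two programmers could both follow the text and report clearly different precision for the same data. If recruitment fell short, the intervals would not show the lost information.

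**Working it through.** **Does 3,000 match the plan?** The planned units are 540 households, 540 x 4 = 2,160 people and, if everyone has both times, 2,160 x 2 = 4,320 rows. None equals 3,000. The allocation table in section 9.2 as printed adds to 180 + 180 = 360 households, or 360 x 8 = 2,880 rows, which is close, but its heading says 540 households.

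**Whole-household draws.** With n households in the data and m drawn, width ratio = sqrt(n/m), and coverage of a nominal 95% interval = 2 x Phi(1.96 x ratio) - 1. Neither depends on the ICC or on attendance rates. With n = 540 households of 4 and rows at both times:

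| Meaning of 3,000 | Households drawn | Ratio | Coverage |
|---|---|---|---|
| Rows | 3,000/8 = 375 | 1.20 | 98% |
| People | 3,000/4 = 750 | 0.85 | 90% |
| Households | 3,000 | 0.42 | 59% |

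**Time 2 rows only for Time 1 attenders.** With attendance a, there are 2,160 x (1 + a) rows, so the row reading gives ratio = sqrt(2,160 x (1 + a)/3,000) = sqrt(0.72 x (1 + a)). The plan gives no value for a:
- a = 0: 0.85
- a = 0.30: 0.97
- a = 0.39: 1.00
- a = 0.50: 1.04
- a = 1: 1.20

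**Household size (both times for everyone).** At an assumed mean of 3, the row reading draws 500 households (1.04) and the people reading 1,000 (0.73). At the minimum of 2, they draw 750 (0.85) and 1,500 (0.60). The row reading thus changes direction.

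**Rows drawn singly.** Of 3,000 rows, about 1,500 are at Time 2, or 750 per level of a factor. The data have 270 households, or 1,080 people, per level, with design effect 1 + 3 x ICC. For a Time 2 contrast, ratio = sqrt((1/750)/((1 + 3 x ICC)/1,080)).
- ICC 0.9, the edge of the plan's own assumption: 0.62, coverage about 78%.
- ICC 0.5 (assumed): 0.76. ICC 1.0: 0.60.
- For a time-by-arm change at ICC 0.9, the ratio also depends on the correlation of household means across times, which the plan does not give: 0.62 at zero, 1.0 at about 0.61, and about 3.8 at 0.97.

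**In percentage points (illustration).** Assume Time 2 rates of 50% and 60%, ICC 0.9 and 270 households per factor level. The correct half-width is 1.96 x sqrt((0.25 + 0.24) x 0.925/270) = 8.0 points, where 0.925 = (1 + 3 x 0.9)/4. Multiplying by the ratios gives 9.6 (rows, whole households), 6.8 (people), 5.0 (single rows) and 3.4 (households).

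**Shortfall.** With 270 households of 4 and both times, the row reading still draws 375. Correct width rises by sqrt(540/270) = 1.41 while the bootstrap width stays where it was, so the ratio falls from 1.20 to sqrt(270/375) = 0.85.

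**Simulation.** This used percentile intervals, 540 households of 4, ICC 0.9, 50% against 60%, and 1,500 datasets of 1,000 resamples. Coverage was 94.4% when 540 households were drawn, 97.8% for rows by household, 90.0% for people, 77.3% for single rows and 60.6% for 3,000 households. It used raw Time 2 proportions and did not refit the mixed model.

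**The case against.** The best defence is that the text has a natural reading, under which it may be about right. In a two-time individual-level model an observation is a person-visit row, and clustering by household implies whole-household draws. If Time 2 rows are kept only for first-test takers, as section 9.1 can be read, the ratio is near 1 for attendance between roughly 30% and 50%. The same holds for a mean household size of 3 with both times for everyone, or for the 360 households in the printed table (sqrt(360/375) = 0.98).

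This stands, and it rules out two tempting inferences. A reader might conclude that no reading gives a nominal interval. The documents do not support that, because they fix neither the analysis set nor household size, and 4,320 rows is itself an inference from section 7.1. A reader might also conclude that the intervals mostly overstate precision. That rests on counting readings. The best-supported one is conservative at the full planned size, the 3,000-household reading has least support, and the single-row reading gives little effect to the household clause and errs in a known direction only for a Time 2 contrast.

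The defence does not rescue the rule. Section 9.4.1 conditions the models for Hypotheses 1r to 3r on Time 1 attendance but does not say so for 4a and 4b, and section 7.1 points to the full cohort. Even where the ratio is near 1, it is so because recruitment, attendance and household size happen to meet a constant.

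**Conclusion.** The concern holds as a defect in the resampling rule. The fixed 3,000 gives correct H4r intervals only if the data happen to hold about that many of the intended unit and whole households are drawn, and it does not respond to recruitment.

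At 540 households of 4, the best-fitting reading is 20% too wide (98% coverage) with both times for everyone, and between 0.85 and 1.20 of the correct width if Time 2 rows depend on Time 1 attendance. The people reading is 0.85 (90%). The larger errors, 0.42 and 0.62, belong to less supported readings. Size and direction therefore depend on the unit, the analysis set and household size.

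The effect is limited to reported precision. Model coefficients and the equality-of-coefficients tests do not use the bootstrap, and the plan attaches no decision rule to these intervals, so no trial-level error rate follows. The whole-household ratios are exact in n and m; the coverages assume approximate normality.

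**What to change.** In section 9.4.1, replace the 3,000 observations with wording to this effect: in each of 2,000 resamples, whole households are drawn with replacement, as many as the Model 4 analysis dataset contains (optionally within randomised arm). All members and all their rows at both testing times are kept, a household drawn more than once receives a new ID each time, and the model is refitted. State the interval type, for example the 2.5th to 97.5th percentiles of the resampled differences. Say in the same place whether people who did not attend Time 1 have Time 2 rows. The width ratio is then 1 for any recruitment total or household size.

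If 3,000 is deliberate, state its unit, draw whole households, and multiply the bootstrap standard error by sqrt(households drawn / households in the data).

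The cost is a short SAP edit and modest reprogramming, with no new data.

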9.1 STATISTICAL HYPOTHESES

The figure below provides a conceptual diagram for thinking about what factors may influence testing take-up and retesting. Testing take-up would depend on several factors, including prior beliefs about infection, health literacy, information networks, health conditions, demographics and socio-economics. We have the following hypothesis based on analysis of literature on testing for HIV and Hepatitis as well as preliminary analysis of data from our prior study:

Hypothesis 1: Those who believe that they have been infected in the past would be more likely agree to testing to confirm that they have antibodies and potential immunity; **Hypothesis 2:** People with poor health literacy will be less likely to agree to testing as they might find it daunting to understand what the test does and how to interpret results; **Hypothesis 3:** Those who are risk averse would be more likely to agree to testing as it reduces uncertainty about serostatus; **Hypothesis 4:** Those with preexisting health conditions would be more likely to agree to testing as they face higher risks from COVID-19 and thus have more to gain from learning serostatus; **Hypothesis 5:** Minorities and those in lower socio-

economic strata would be less likely to agree to testing due to fear of discrimination, lack of trust in health care/research, poor past experience, and perception of being at low risk of infection. We also generate hypotheses for facilitators to retesting (r) relative to those who take a first test **Hypothesis 1r:** Persons who practice low COVID-19 mitigation, exhibit risk-seeking and have high exposure risk may respond to a lottery retest incentive. **Hypothesis 2r:** Those persons with low income, unemployed, or have high stress or anxiety may respond most to insurance of incentives. **Hypothesis 3r:** Persons who are sero+ at baseline will be less likely to return for a retest. **Hypothesis 4r:** Lottery insurance and family messaging will induce higher retesting rates. Hypotheses 1-5 are covariates that may affect agreeing to the test. Hypotheses 1r and 2r refer to heterogeneity of treatment effects for retesting, while 3r and 4r are main effects on retesting.

Conceptual diagram

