9.4 STATISTICAL ANALYSES

9.4.1 GENERAL APPROACH

Aim 1 (Hypotheses 1-5): Data from the baseline survey combined with data on which heads of households attended Time 1 testing will be used to address Aim 1. In particular, we will estimate logistic regressions where the dependent variable will be the binary indicator whether the head of household attended Time 1 testing (yes vs. no). The key independent variables will include: 1) prior COVID-19 testing, 2) which SARS-CoV-2 information sources are most trusted, 3) risk aversion, 4) heads of households or family member diagnosis of a health condition (e.g., diabetes, hypertension) and, 5) race/ethnicity, income, discriminatory incidences, household receipt of Supplemental Nutrition Assistance Program (SNAP) or Supplemental Security Income (SSI) benefits, and citing money as the biggest vaccine barrier.

$$\pi = \beta_0 + \beta_1 x_i + \varepsilon_i \quad [1]$$

$\pi = \ln\left(\frac{p}{1-p_i}\right)$; p_i , is the probability of attending Time 1 testing, by head of household i , and β_1 is each head of household reported social determinant of health. This will allow us to identify significant social and behavioral determinants for heterogeneity of effects (currently hypothesized in Hypotheses 1-5 above).

Aim 2 (Hypotheses 1r-4r): Aim 2 will involve regressing Time 2 retesting (yes vs. no) on the following items for Hypotheses 1r-4r: 1r) risk aversion, essential worker status, access to personal protective equipment, and risky forms of transportation (e.g., personal vehicle, carpool, bus), 2r) income, discriminatory incidences, employment status, whether heads of households personally, or other family members suffer from depression and/or mental health issues, and household receipt of Supplemental Nutrition Assistance Program (SNAP) or Supplemental Security Income (SSI) benefits, 3r) Time 1 seropositivity status and, 4r) the Financial Incentive and Messaging study arms.

$$\pi = \beta_0 + \beta_1 x_i + \beta_2 x_i + \beta_3 x_i + \varepsilon_i \quad [2]$$

For Hypotheses 1r-2r, $\pi = \ln\left(\frac{p}{1-p_i}\right)$, is the probability of Time 2 attendance by head of household i given they attended Time 1 testing; β_1 is the main effect of the head of household reported characteristic, β_2 is the main effect of the Financial Incentive, where the lottery condition is the reference, and β_3 is the interaction between the head of household reported social determinant of health and Financial Incentive.

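### Hypothesis 4r concerns retesting, but the tests named for Models 4a and 4b compare changes from Time 1, and none tests either factor's effect at Time 2

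*Combined protocol and SAP*

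**What the plan says.** - **Hypothesis.** Section 9.1 predicts higher retesting with lottery insurance and with family messaging, and classifies the hypotheses thus: "while 3r and 4r are main effects on retesting". It introduces the retest hypotheses with "We also generate hypotheses for facilitators to retesting (r) relative to those who take a first test".
- **Outcome.** Section 9.4.1 states "Aim 2 will involve regressing Time 2 retesting (yes vs. no) on the following items for Hypotheses 1r-4r", the last item being "4r) the Financial Incentive and Messaging study arms". Section 9.2 projects a 10-point difference between intervention and control in repeat testing.
- **Models.** For H4r, Section 9.4.1 models attendance at both times, with Time 1 as reference and a random household intercept. In Model 4a, β_2 and β_3 are labelled main effects of incentives and messaging, and "β_4 is the interaction between testing time and Financial Incentives; β_5 is the interaction between testing time and Messaging". In Model 4b the reference is personal messaging with lottery. The other arms, in order, are "personal messaging and loss protection, family messaging and lottery, family messaging and loss protection", with main effects β_2 to β_4 and time interactions β_5 to β_7.
- **Tests.** The team "will test differences in effect sizes for Model 4a (β_4 vs. β_5) and 4b". The pairs listed for 4b are β_5 vs β_6, β_5 vs β_7 and β_6 vs β_7.
- **Bootstrap.** Households are resampled "to bootstrap 95% confidence intervals for probability differences". No time point or pair of groups is given.
- **Timing.** Randomisation is at the start of the study (Section 6.3), and participants learn their arm on the recruitment call (Section 6.1.2). Section 4.1 predicts that family framing raises both first uptake and repeat testing.
- **Who can attend.** Section 7.1 offers the second wave to people who declined the first. Section 8.1 gives Study IDs to household members interested in testing.

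**The concern.** Sections 9.1 and 9.2 and the Aim 2 sentence in 9.4.1 all describe a between-arm effect at Time 2, but the model text does not carry this into a named contrast. The contents page lists an analysis section for the primary endpoint; the body has none, and its Section 9.4.2 covers the secondary endpoints. Section 3 lists several effects without ranking them.

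Two things are at stake. The estimate that answers the primary objective could be chosen after the data are seen. And Time 1 attendance is not a neutral baseline: it follows disclosure of the arm, and messaging is predicted to move it. An analysis of change then removes part of the effect that H4r is about.

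**Working it through.** **1. What each coefficient measures.** With time interactions in the model and Time 1 as reference:

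- Model 4a: β_2 and β_3 are effects at Time 1, whatever their label. β_4 and β_5 are differences in log-odds change from Time 1 to Time 2. The Time 2 effects are β_2+β_4 (incentives) and β_3+β_5 (messaging).
- Model 4b: the Time 2 effects of the three arms against reference are β_2+β_5, β_3+β_6 and β_4+β_7.

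**2. What each named test asks.**

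| Test | Question |
|---|---|
| 4a: β_4 vs β_5 | Do the two factors alter change by different amounts? Null if both work equally or neither works |
| 4b: β_5 vs β_6 | Same kind of question; both factors differ between the two arms |
| 4b: β_5 vs β_7 | Family vs personal, under insurance only, on change |
| 4b: β_6 vs β_7 | Insurance vs lottery, under family messaging only, on change |

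The last two isolate one factor and bear on H4r, but only through change and at one level of the other factor. No row is a Time 2 contrast unless the arms are equal at Time 1.

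**3. The plan's own figures.** Section 9.2 gives ±3 points as detectable for H4r. It cannot be reproduced, because the control rate, alpha and power for H4r are not stated, and nothing below uses it. The 10-point projection is used as the Time 2 effect.

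**4. Size of the subtraction.** Assumed marginal rates, none from the documents: reference arm 60% at Time 1 and 40% at Time 2; messaging raises Time 2 to 50%.

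Interaction = log OR at Time 2 − log OR at Time 1. The Time 2 log OR is logit(0.50) − logit(0.40) = 0.405.

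| Messaging at Time 1 | log OR at Time 1 | Interaction |
|---|---|---|
| 60% to 60% | 0 | 0.405 |
| 60% to 65% | 0.214 | 0.192 (from unrounded values) |
| 60% to 70% | 0.442 | -0.036 |

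**5. Readings of the probability difference for messaging**, 60% to 70% case: between arms at Time 2, 0.50 − 0.40 = +10 points; difference in change, (0.50 − 0.70) − (0.40 − 0.60) = 0; within family messaging over time, 0.50 − 0.70 = −20 points.

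**6. Rejection rates (illustrative).** Simulation with four arms of 135 households of 4, shared household intercept with SD 2, two-sided 5%, both factors adding 10 points at Time 2:

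| Messaging effect at Time 1 | β_5 vs β_7 | β_3+β_5 vs 0 |
|---|---|---|
| none | 88% | 88% |
| +5 points | 30% | 91% |
| +10 points | 5% | 91% |

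A normal approximation with intra-cluster correlation 0.9 and cross-time correlation 0 to 0.65 gives β_5 vs β_7 as 23% to 53%, 9% to 16% and 5%, against 68% for the Time 2 contrast. With no Time 1 effect, β_4 vs β_5 rejects in 4% to 5% although both factors work.

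**7. Population.** Let d be the share of first-wave decliners who attend the second wave, equal in all arms. Messaging lifts Time 1 to 70%; incentives leave it at 60%; both lift Time 2 to 50%. Rate among first-testers = [Time 2 rate − d × (1 − Time 1 rate)] / Time 1 rate; completing both tests is the numerator.

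| Definition of retesting | Reference | Messaging | Incentives |
|---|---|---|---|
| Time 2 attendance, all randomised | 40% | 50% (+10) | 50% (+10) |
| First-testers, d = 0 | 66.7% | 71.4% (+4.8) | 83.3% (+16.7) |
| First-testers, d = 0.2 | 53.3% | 62.9% (+9.5) | 70.0% (+16.7) |
| Both tests, all randomised, d = 0.2 | 32% | 44% (+12) | 42% (+10) |

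Models 4a and 4b cannot be restricted to first-testers: Time 1 attendance would then be constant and the time interactions could not be estimated.

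**The case against.** The strongest reply is that the equality tests were never meant as the test of H4r. Section 9.4.1 presents them as comparisons of effect sizes, which reads as a follow-up to the estimated effects. That stands: the fact that β_4 vs β_5 cannot see two equal effects is no defect in a comparison of effects. Tests of β_4 and β_5 against zero also come with the fitted model, and if no factor affects Time 1 they can be more powerful (99% against 88% to 89% in the SD 2 simulation; 40% to 82% against 68% in the approximation). But the plan does not name them, and β_5 against zero loses the Time 1 messaging effect in the same way.

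The magnitude is also open to challenge. Section 4.1 predicts a direction at Time 1, not a size, and the +10 case almost exactly cancels the Time 2 effect. Incentives were given no Time 1 effect, although that arm too is disclosed on the recruitment call. The simulation used Wald tests with model covariance, which may differ from the cited equality test. The rejection rates therefore illustrate the problem; they do not forecast results.

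A reader might infer three stronger claims that the documents do not support:

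- *H4r has no stated hypothesis.* Outcome, direction and type of effect are stated; the contrast is missing.
- *The plan will wrongly rank incentives above messaging.* That requires the two effects on retesting to be equal, which in the worked case holds for Time 2 attendance among all randomised. Among first-testers incentives really are ahead (+16.7 against +4.8 or +9.5).
- *Time 2 attendance among all randomised is the only valid endpoint.* It keeps the randomised comparison, but because first-wave decliners may attend the second wave, it counts some first tests as retests.

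**Conclusion.** The concern holds. H4r is a between-arm effect on retesting, and Section 9.4.1 names no test of either factor at Time 2, no time point or groups for the probability differences, and no settled population. Contrasts of change understate messaging's effect on retesting if messaging raises first uptake, as the protocol predicts. In the worked case this is true for Time 2 attendance among all randomised and among first-testers alike. Incentives carry no such predicted bias, since no effect of incentives on first uptake is predicted.

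The size rests on assumed attendance rates: about half the log-odds effect is lost if messaging adds 5 points at Time 1, and all of it at 10. Rejection rates further depend on assumed correlations. Any misranking of the two factors is conditional on how the H4r population is defined. This should be corrected before the data are analysed, because it decides which number answers the primary objective.

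**What to change.** 1. In Model 4a, name β_2+β_4 (incentives) and β_3+β_5 (messaging), each against zero, as the H4r tests. Say whether H4r needs one or both, and how multiplicity is handled. Keep the Model 4b arm contrasts and all equality tests as secondary or exploratory.
2. Define the bootstrapped probability differences as between-arm differences at Time 2.
3. Report Time 1 uptake by arm separately (β_2 and β_3 in Model 4a).
4. Reconcile the H4r population across Sections 9.1, 9.4.1 and 7.1. State whether retesting means attending at Time 2 or completing both tests. Report an all-randomised and a first-tester analysis, noting that only the former keeps the randomised comparison.

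The cost is mainly wording, since the contrasts come from models already planned. The team must confirm that denominators exist for people who declined testing, given how Study IDs are assigned in Section 8.1. The downsides are a little more analysis and possibly less power than the interaction test if no factor affects Time 1.

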7.1 DISCONTINUATION OF STUDY INTERVENTION/EXPERIMENTAL MANIPULATION

Participants who decline testing initially will be offered an exit survey which will ask them for reasons for declining. We will longitudinally follow the initial cohort that completed baseline survey (including people who declined testing in wave 1) and offer an additional wave of testing 6 months after the first wave.

Participants can choose to withdraw from the study at any time, and this will be documented in their REDCap record. When a subject discontinues Wave 2 retesting but not from the study, remaining study procedures (data analysis) will be completed as indicated by the study protocol.

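### The equality tests in Models 4a and 4b have no stated variance; with the single-intercept model's own standard errors they can be miscalibrated in either direction

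*Combined protocol and SAP*

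**What the plan says.** Section 9.4.1 fits Models 4a and 4b as logistic models of each individual's attendance at Time 1 and Time 2. In both, η "is the random intercept for each household", and nothing else in the model links members or visits: there is no household-by-visit term and no person term. In 4a, β4 is time by incentive and β5 is time by messaging. In 4b, β5 to β7 are time by arm, all against the same reference arm (personal message, lottery).

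Two inferential tools follow. The first is a bootstrap that will "select 3,000 observations, 2,000 times, clustered by household to bootstrap 95% confidence intervals for probability differences". For the second, the team "will test differences in effect sizes for Model 4a" (β4 against β5) and for three pairs in 4b, "using equality of regression coefficients tests", with a pointer to reference 6. No standard error or covariance is named for these tests. The only standard-error formula in the paragraph, √(P(1−P)/N), belongs to the number needed to intervene on and has no clustering term.

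Section 9.2 states: "Randomization will be clustered by family". It adds: "For the purposes of power analyses, we assume high Intra Cluster Correlation within family on uptake of repeat testing (>0.90"). Section 7.1 states: "We will longitudinally follow the initial cohort that completed baseline survey (including people who declined testing in wave 1"), and those people are offered the second wave. Hypothesis 4r in Section 9.1 reads: "Lottery insurance and family messaging will induce higher retesting rates".

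**The concern.** Every coefficient being compared is a between-visit contrast of arms that were allocated by family. The noise that matters is therefore how much a household's attendance changes from Time 1 to Time 2. A single intercept common to both visits absorbs only the part of household behaviour that does not change. If a family declines the first wave together and comes to the second together, the model has no term for that shift and treats it as separate events in each member. The model-based standard error is then too small. If instead households are stable and individuals are stable too, the residual variance is overstated for a change score and the standard error is too large.

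These are the only coefficient tests named for 4a and 4b. They would carry any statement that incentives work better than messaging, or that one arm beats another. The results could also show a household-clustered interval beside a test that ignores household-level change.

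**Working it through.** The plan states no error rate for these tests, so there is no figure to reproduce. (The 3-point detectable difference in Section 9.2 concerns intervention against control and does not bear on this point.)

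**Inputs from the plan.** 540 households and 2,160 people, so 4 per household (Section 9.2); 2 x 2 design (Section 1.1); randomization by family and intra-cluster correlation (ICC) above 0.90 for repeat testing (Section 9.2). The two-sided 5% level is inferred from the 95% intervals.

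**Assumed, because the plan is silent.** Model-based standard errors; equal arms of 135 households; the same ICC at both visits; the attendance rates; the share of household variance common to both visits; no true arm effect.

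**Step 1: linear analogue.** Take total variance 1, visit-specific household variance v = ICC × (1 − 0.9) for a cross-visit correlation of 0.9, and residual variance e = 1 − ICC. For 4 members and 2 visits:
- between-visit mean square: B = 4v + e
- pooled residual that the single-intercept model uses: W = (B + 6e)/7
- true variance over model variance: B/W
- false-positive rate: 2[1 − Φ(1.96/√(B/W))]

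| ICC | v | e | B | W | B/W | False positives |
|---|---|---|---|---|---|---|
| 0.90 | 0.09 | 0.10 | 0.46 | 0.151 | 3.04 | 26.1% |
| 0.70 | 0.07 | 0.30 | 0.58 | 0.340 | 1.71 | 13.3% |
| 0.50 | 0.05 | 0.50 | 0.70 | 0.529 | 1.32 | 8.9% |
| 0.30 | 0.03 | 0.70 | 0.82 | 0.717 | 1.14 | 6.7% |

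If v = 0, B/W = 1 and the test is at 5%. Now let half the non-household variance be stable within person (s): W = [B + 3(2s + e) + 3e]/7. At ICC 0.50, s = e = 0.25 and v = 0.05, B = 0.45, W = 0.493, B/W = 0.91, giving 4.0%. With v = 0, B = 0.25, W = 0.464, B/W = 0.54, giving 0.8%. The error can go either way.

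**Step 2: Model 4a itself.** Random-intercept logistic fits by maximum likelihood, 1,000 simulated trials per cell (Monte Carlo error about ±1.4 points at 5%), logit-scale ICC, attendance 60% then 50%, z-test of β4 − β5 with model-based errors. False positives by share of household variance common to both visits:

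| ICC | 100% | 90% | 50% |
|---|---|---|---|
| 0.90 | 4.8% | 19.6% | 28.9% |
| 0.70 | 3.0% | 9.5% | 22.6% |
| 0.50 | 5.1% | 7.8% | 14.1% |
| 0.30 | 3.6% | 5.3% | 9.1% |
| 0.90, half of the rest stable within person | 2.2% | 16.9% | 31.9% |
| 0.50, same | 1.7% | 5.0% | 12.6% |
| 0.30, same | 1.4% | 4.0% | 7.2% |

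At ICC 0.90 and 90% shared, other attendance rates gave 19.0% (50% then 50%) and 11.2% (80% then 40%). A separate simulation gave 17.7% for the 60%/50% case, 11.8% with 95% shared, and 5.2% with 100% shared. In that simulation, at 55% then 45%, β4 tested alone rejected 17.7% of the time against 17.6% for the difference, so single time-by-arm coefficients behave the same way.

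**Step 3: Model 4b.** With equal arms of variance s² each, two interactions against a shared reference each have variance 2s² and covariance s². The difference truly has variance 2s², but 4s² if the covariance is dropped. When the model is correct, dropping it gives 2[1 − Φ(1.96 × √2)] = 0.6%; simulation gave 0.5-0.9%. At ICC 0.90, 90% shared, 60% then 50%, the three tests ran at 5.3-6.4% without the covariance and 19.1-19.6% with it. In 4a, including or dropping the covariance hardly matters (within 0.4 points).

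**Step 4: household-cluster-robust variance, covariance included.** Over all scenarios simulated: 3.4-6.8% in 4a and 3.5-6.8% in 4b. In a smaller set of 600 runs, one 4b pair reached 8.5% (80% then 40%).

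**The case against.** The strongest reply is that this is an ambiguity and not an error. The test is specified by citation, and reference 6 may settle the variance and the covariance. It cannot be seen here, so that remains open. What stands is that the plan's own text does not say, and the natural default is the fitted model's output.

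Second, the size rests on inputs that the documents do not give. The 90% share is an assumption, and at 100% with no lasting person-level difference the test is close to nominal. The ICC above 0.90 is offered for power and for repeat testing only, with no scale. This stands, and it is why only conditional ranges are given. Section 7.1 makes household change possible; nothing says how large it is.

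Third, the analysis set for 4a is undefined, and Section 8.1 gives individual study IDs only to members interested in testing. The simulated attendance rates are therefore illustrative. But 4a models attendance at both visits, so it needs people who missed Time 1; otherwise that visit has no variation.

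Fourth, the reach is small. This stands: hypothesis 4r says both interventions raise retesting, not that their effects differ.

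Two stronger readings are tempting. A reader might infer that the plan has a 20% error rate, or as much as 44%. The latter needs ICC 0.90 on the observed yes/no scale and a cross-visit correlation or share of only one half, and no error rate follows without the unstated choice of model-based errors. A reader might also infer that the test of 4r is invalid. The household-clustered bootstrap planned for probability differences speaks against that.

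**Conclusion.** The gap is real and the mechanism is sound, but the consequence is conditional. The single-intercept model's standard errors are right for the 4a comparison only when household propensity is fully stable between visits and there are no lasting person-level differences. Other combinations land near 5% only because two errors offset.

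With model-based errors, logit-scale ICC 0.90, 90% of household variance shared and four members per household, false positives are roughly 11-20%, depending on attendance. At ICC 0.30-0.50 with the same share they are roughly 4-9%. With stable households and stable individuals the test is conservative, at about 1-2%. In 4b the answer also turns on whether the covariance from the shared reference arm is included.

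The point is limited to comparing the incentive effect with the messaging effect and the arms with one another. Hypothesis 4r is not directly affected if judged on the bootstrapped probability differences; it would be if judged on model-based tests of β4 and β5. This is a cheap improvement to the plan and does not show that the main result will be wrong.

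**What to change.** In Section 9.4.1, state that the equality tests for 4a and 4b, and any other test of a time-by-arm coefficient, use one of these:
- a household-cluster-robust covariance matrix, including the covariance between the compared coefficients; or
- a bootstrap that resamples whole households, as many as are in the analysis set, and saves the coefficients from each resample.

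The planned draw of a fixed 3,000 observations should not be reused unchanged for this. If the 4a data held 2,160 × 2 = 4,320 rows (the plan does not give the size), 3,000 rows would be 375 households of eight rows instead of 540. The bootstrap variance would then be 540/375 = 1.44 times too large, and standard errors 1.2 times. A household-by-visit random effect is another route, but it was not simulated.

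The cost is a sentence in the plan and a change to the variance calculation; no new data are needed. The downside is precision: across the scenarios run, the standard error of β4 − β5 became 0.83 to 2.43 times the model-based one, wider where households change between visits and narrower where individuals are stable. Robust calibration was checked mainly with no arm effect; with equal non-zero effects, a linear-probability simulation gave 4.5%.
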